10. ETHICAL CONSIDERATIONS AND ADMINISTRATIVE PROCEDURES

10.1. Investigator Responsibilities

This study will be performed in accordance with ethical principles that originate in the Declaration of Helsinki and conducted in adherence to the study Protocol; GCPs as defined in Title 21 of the US CFR Parts 11, 50, 54, 56, and 312; ICH E6 GCP consolidated guidelines; and local regulatory requirements as applicable to the study locations.

The investigator will be responsible for:

- Permitting study-related monitoring, sponsor audits, IRB/IEC review, and regulatory inspections by providing direct access to source data and other relevant clinical study documents.
 - Monitoring: Qualified representatives of the sponsor or its designee, study monitors, will monitor the study according to a predetermined plan. The investigator must allow the study monitors to review any study materials and subject records at each monitoring visit.
 - Auditing: Qualified representatives of the sponsor or its designee may audit the clinical study site and study data to evaluate compliance with the Protocol, applicable local clinical study regulations, and overall study conduct. The investigator must allow the auditors to review original source records and study documentation for all subjects.
 - Regulatory inspection: Regulatory authorities may conduct an inspection of the study and the site at any time during the development of an investigational product. The investigator and staff are expected to cooperate with the inspectors and allow access to all source documents supporting the eCRFs and other study-related documents. The investigator must immediately notify the sponsor when contacted by any regulatory authority for the purposes of conducting an inspection.
- Obtaining informed consent and ensuring that the study subjects' questions have been answered and the subjects fully understand study procedures:
 - Informed consent must be obtained before any study-related procedures are conducted.

CONFIDENTIAL

CONFIDENTIAL

- Informed consent must be obtained using the IRB/IEC-approved version in a language that is native and understandable to the subject. A template will be provided by the sponsor or its designee. The sponsor or its designee must review and acknowledge the site-specific changes to the ICF template. The ICF must include a statement that the sponsor or its designee and regulatory authorities have direct access to subject records.
- Obtaining approval from the IRB/IEC before the start of the study and for any changes to the clinical study Protocol, important protocol deviations, routine updates, and safety information in accordance with institutional requirements and local law.
 - The investigator is responsible for ensuring that the safety reports provided by the sponsor are reviewed and processed in accordance with regulatory requirements and with the policies and procedures established by the IRB/IEC.
- Adhering to the Protocol as described in this document and agreeing that changes to the Protocol procedures, with the exception of medical emergencies, must be discussed and approved, first, by the sponsor or its designee and, second, by the IRB/IEC. Each investigator is responsible for enrolling subjects who have met the specified eligibility criteria.
- Retaining records in accordance with all local, national, and regulatory laws, but for a minimum period of at least 2 years after the last marketing application approval in an ICH region and until there are no pending or contemplated marketing applications in an ICH region, or if not approved, 2 years after the termination of the test article for investigation to ensure the availability of study documentation should it become necessary for the sponsor or a regulatory authority to review.
 - The investigator must not destroy any records associated with the study without receiving approval from the sponsor. The investigator must notify the sponsor or its designee in the event of accidental loss or destruction of any study records. If the investigator leaves the institution where the study was conducted, the sponsor or its designee must be contacted to arrange alternative record storage options.
 - All eCRF data entered by the site (including audit trail), as well as computer hardware and software (for accessing the data), will be maintained or made available at the site in compliance with applicable record retention regulations. The sponsor will retain the original eCRF data and audit trail.

10.2. Accountability, Handling, and Disposal of Study Drug

The investigator is responsible for drug accountability at the study site; however, some of the drug accountability duties may be assigned to an appropriate pharmacist or other designee. Inventory and accountability records must be maintained and readily available for inspection by the study monitor and are open to inspection at any time by any applicable regulatory authorities. The investigator or designee must maintain records that document:

- Delivery of study drug to the study site.
- Inventory of study drug at the site.

CONFIDENTIAL

CONFIDENTIAL

- Subject use of the study drug including pill or unit counts from each supply dispensed.
- Return of study drug to the investigator or designee by subjects.

The investigational product must be used only in accordance with the Protocol. The investigator will also maintain records adequately documenting that the subjects were provided the specified study drug. These records should include dates, quantities, and any available batch or serial numbers or unique code numbers assigned to the investigational product and study subjects.

Completed accountability records will be archived by the site. The investigator or designee will be expected to collect and retain all used, unused, and partially used containers of study drug until verified by the study monitor (unless otherwise agreed to by the sponsor). At the conclusion of the study, the investigator or designee will oversee shipment of any remaining study drug back to the sponsor or its designee for destruction according to institutional standard operating procedures. If local procedures mandate on-site destruction of investigational supply, the site should (where local procedures allow) maintain the investigational supply until the study monitor inspects the accountability records in order to evaluate compliance and accuracy of accountability by the investigative site. At sites where the study drug is destroyed before monitor inspection, the monitors rely on documentation of destruction per the site SOP.

10.3. Data Management

Data management will be performed in a validated EDC system. The investigator will be provided with access to an EDC system so that an eCRF can be completed for each participant.

The site will be provided with eCRF completion guidelines for instructions on data entry in the eCRF. The study monitor will reference the Monitoring Plan in order to ensure that each issue identified is appropriately documented, reported, and resolved in a timely manner in accordance with the plan's requirements. Other data outside the EDC system required in the study conduct of the Protocol such as documents or results transmitted to the sponsor via a central laboratory or specialized technical vendors, and as designated by the sponsor, will have their own data flow management plans, or study charters, or biomarker plans, as applicable.

The sponsor (or designee) will be responsible for:

- Managing the integrity of the data and the quality of the conduct of the study, such as ensuring that study monitors perform ongoing source data verification to confirm that data entered into the eCRF by authorized site personnel are accurate, complete, and verifiable from source documents; that the safety and rights of participants are being protected; and that the study is being conducted in accordance with the currently approved Protocol and any other study agreements, ICH GCP, and all applicable regulatory requirements.
- Managing and reconciling the data generated, and/or collected including documents and results such as laboratory or imaging data analyzed centrally by a designated vendor of the sponsor.

CONFIDENTIAL

CONFIDENTIAL

The investigator will be responsible for:

- Recording, or ensuring the recording of, all relevant data relating to the study in the eCRF.
- Delivering, or ensuring the delivery of, all other results, documents, data, know-how, or formulas relating to the study to the sponsor or designee electronically and/or centrally (e.g., laboratory data, imaging data, biomarker data, photographs, diary data), or as otherwise specified in the Protocol.
- Verifying that data entries are accurate and correct by physically or electronically signing the eCRF.
- Maintaining accurate documentation (source data) that supports the information entered in the eCRF, or sent to a central vendor designated by the sponsor, or as described in other study and data flow manuals.
 - Source documents provide evidence for the existence of the participant and substantiate the integrity of the data collected. Source documents are filed at the investigator's site.
 - Data entered in the eCRF that are transcribed from source documents must be consistent with the source documents or the discrepancies must be explained. The investigator may need to request previous medical records or transfer records, depending on the study. Also, current applicable medical records must be available.
- May have responsibility for sending participants' data, either as unique samples, or copies, or photographs, to be evaluated centrally or analyzed centrally, or both, by a qualified vendor designated by the sponsor.
- Permitting study-related monitoring, sponsor audits, IRB/IEC review, and regulatory inspections by providing direct access to source data and other relevant clinical study documents.
 - Monitoring: Qualified representatives of the sponsor or its designee, study monitors, will monitor the study according to a predetermined plan. The investigator must allow the study monitors to review any study materials and participant records at each monitoring visit.
 - Auditing: Qualified representatives of the sponsor or its designee may audit the clinical study site and study data to evaluate compliance with the Protocol, applicable local clinical study regulations, and overall study conduct. The investigator must allow the auditors to review original source records and study documentation for all participants.
 - Regulatory inspection: Regulatory authorities may conduct an inspection of the study and the site at any time during the development of an investigational product. The investigator and staff are expected to cooperate with the inspectors and allow access to all source documents supporting the eCRFs and other study related documents. The investigator must immediately notify the sponsor when contacted by any regulatory authority for the purposes of conducting an inspection.

CONFIDENTIAL

CONFIDENTIAL

10.4. Data Privacy and Confidentiality of Study Records

The investigator and the sponsor, or its designee, must adhere to applicable data privacy laws and regulations. The investigator and the sponsor, or its designee, are responsible for ensuring that sensitive information is handled in accordance with local requirements (eg, HIPAA). Appropriate consent and authorizations for use and disclosure and/or transfer (if applicable) of protected information must be obtained.

Subject names will not be supplied to the sponsor or its designee, if applicable. Only the subject number and subject's initials will be recorded in the eCRF, where permitted; if the subject's name appears on any other document (eg, laboratory report), it must be obliterated on the copy of the document to be supplied to the sponsor or its designee. Study findings stored on a computer will be stored in accordance with local data protection laws. The subjects will be informed that representatives of the sponsor or its designee, IRB or IEC, or regulatory authorities may inspect their medical records to verify the information collected, and that all personal information made available for inspection will be handled in strictest confidence and in accordance with local data protection laws.

10.5. Financial Disclosure

Before study initiation, all clinical investigators participating in clinical studies subject to FDA Regulation Title 21 Code of Federal Regulations (CFR) Part 54 – Financial Disclosure by Clinical Investigators (ie, "covered studies") are required to submit a completed Clinical Investigator Financial Disclosure form that sufficiently details any financial interests and arrangements that apply. For the purpose of this regulation, "clinical investigator" is defined as any investigator or subinvestigator who is directly involved in the treatment or evaluation of research subjects, including the spouse and each dependent child of the clinical investigator or subinvestigator. These requirements apply to both US and foreign clinical investigators conducting covered clinical studies.

Any new clinical investigators added to the covered clinical study during its conduct must also submit a completed Investigator Financial Disclosure Form. During a covered clinical study, any changes to the financial information previously reported by a clinical investigator must be reported to the sponsor or its designee. At the conclusion of the covered clinical study, the clinical investigators will be reminded of their obligations. In the event that the clinical investigator is not reminded, they nevertheless will remain obligated to report to the sponsor or its designee any changes to the financial information previously reported, as well as any changes in their financial information for a period of 1 year after completion of the covered clinical study.

CONFIDENTIAL

CONFIDENTIAL

10.6. Publication Policy

By signing the study Protocol, the investigator and his or her institution agree that the results of the study may be used by the sponsor, Incyte Corporation (Incyte), for the purposes of national and international registration, publication, and information for medical and pharmaceutical professionals. Study results will be published in accordance with applicable local and national regulations. If necessary, the authorities will be notified of the investigator's name, address, qualifications, and extent of involvement. The terms regarding the publication of study results are contained in the agreement signed with the sponsor or its designee. A signed agreement will be retained by the sponsor or its designee.

CONFIDENTIAL

CONFIDENTIAL

APPENDIX A. INFORMATION REGARDING EFFECTIVENESS OF CONTRACEPTIVE METHODS

For Subjects Participating in the Study:

The following methods that can achieve a failure rate of less than 1% per year when used consistently and correctly are considered as highly effective birth control methods.

Such methods include:

- Combined (estrogen and progestogen containing) hormonal contraception associated with inhibition of ovulation¹
 - oral
 - intravaginal
 - transdermal
- Progestogen-only hormonal contraception associated with inhibition of ovulation¹
 - oral
 - injectable
 - implantable²
- Intrauterine device (IUD)²
- Intrauterine hormone-releasing system (IUS)²
- Bilateral tubal occlusion²
- Vasectomised partner^{2,3}
- Sexual abstinence⁴

¹ Hormonal contraception may be susceptible to interaction with the IMP, which may reduce the efficacy of the contraception method.

² Contraception methods that in the context of this guidance are considered to have low user dependency.

³ Vasectomised partner is a highly effective method provided of avoiding pregnancy that partner is the sole sexual partner of the WOCBP trial participant and that the vasectomised partner has received medical assessment of the surgical success.

⁴ In the context of this guidance, sexual abstinence is considered a highly effective method only if defined as refraining from heterosexual intercourse during the entire period of risk associated with the study treatments. The reliability of sexual abstinence needs to be evaluated in relation to the duration of the clinical trial and the preferred and usual lifestyle of the subject.

Source: [CTFG 2014](#).

APPENDIX B. PHARMACOKINETIC ANALYTICAL PARAMETERS

C_{ave}	Average steady-state plasma concentration ($AUC_{0-12h}/12h$ or $AUC_{0-24h}/24h$)
C_{max}	Maximum observed plasma concentration
C_{min}	Minimum observed plasma concentration during the dosing interval
T_{max}	Time to maximum plasma concentration
AUC_{0-t}	Area under the single-dose plasma concentration-time curve from Hour 0 to the last quantifiable measurable plasma concentration, calculated by the linear trapezoidal rule for increasing concentrations and the log trapezoidal rule for decreasing concentrations
$AUC_{0-\tau}$ (ie, AUC_{0-12h} or AUC_{0-24h})	Area under the steady-state plasma concentration-time curve over 1 dosing interval (ie, from Hour 0 to 12 for BID administration or from Hour 0 to 24 for QD administration), calculated by the linear trapezoidal rule for increasing concentrations and the log trapezoidal rule for decreasing concentrations
λ_z	Apparent terminal phase disposition rate constant, where λ_z is the magnitude of the slope of the linear regression of the log concentration versus time profile during the terminal phase
$t_{1/2}$	Apparent plasma terminal phase disposition half-life (whenever possible), where $t_{1/2} = (\ln 2) / \lambda_z$
Cl/F	Oral dose clearance
V_z/F	Apparent oral dose volume of distribution
Fluctuation	Steady-state fluctuation ($[C_{max} - C_{min}]/C_{ave}$)

In addition, the following PK parameters may be calculated, whenever possible, for each subject based on the urine INCB053914 concentrations:

A_e	Amount of drug excreted in the urine over sampling interval
Cl_r	Renal clearance, where $Cl_r = A_e/AUC$
% Excreted or f_e	percent excreted in the urine, where % Excreted = 100 ($A_e/dose$)

Pharmacokinetic calculations will be performed, if appropriate, using commercial software such as WinNonlin (Pharsight Corporation, Cary, NC). Additional details of analyses will be described in the Statistical Analysis Plan.

CONFIDENTIAL

CONFIDENTIAL

**APPENDIX C. EASTERN COOPERATIVE ONCOLOGYGROUP (ECOG)
PEFORMANCE STATUS**

Grade	Performance Status
0	Fully active, able to carry on all predisease performance without restriction.
1	Restricted in physically strenuous activity but ambulatory and able to carry out work of a light or sedentary nature, eg, light house work, office work.
2	Ambulatory and capable of all self-care but unable to carry out any work activities. Up and about more than 50% of waking hours.
3	Capable of only limited self-care, confined to bed or chair more than 50% of waking hours.
4	Completely disabled. Cannot carry on any self-care. Totally confined to bed or chair.
5	Dead.

Source: [Oken et al 1982](#).

CONFIDENTIAL

[figure not shown]
CONFIDENTIAL

APPENDIX D. INTERNATIONAL WORKING GROUP RESPONSE CRITERIA FOR ACUTE MYELOID LEUKEMIA

Response Category	Response Definition
Complete remission (CR) ¹	Bone marrow blasts < 5 percent; absence of blasts with Auer rods; absence of extramedullary disease; absolute neutrophil count > 1.0 × 10 ⁹ /L (1000/μL); platelet count > 100 × 10 ⁹ /L (100,000/μL); independence of red cell transfusions
CR with incomplete recovery (CRi)	All CR criteria except for residual neutropenia (< 1.0 × 10 ⁹ /L [1000/μL]) or thrombocytopenia (< 100 × 10 ⁹ /L [100,000/μL])
Morphologic leukemia-free state	Bone marrow blasts < 5 percent; absence of blasts with Auer rods; absence of extramedullary disease; no hematologic recovery required
Partial remission (PR)	All hematologic criteria of CR; decrease of bone marrow blast percentage to 5 to 25 percent; and decrease of pretreatment bone marrow blast percentage by at least 50 percent
Cytogenetic CR (CRC)	Reversion to a normal karyotype at the time of morphologic CR (or CRi) in cases with an abnormal karyotype at the time of diagnosis; based on the evaluation of 20 metaphase cells from bone marrow
Molecular CR (CRm)	No standard definition; depends on molecular target
Treatment failure	
Resistant disease (RD)	Failure to achieve CR or CRi or PR (Phase 1 trials); only includes patients surviving ≥ 7 days following completion of initial treatment, with evidence of persistent leukemia by blood and/or bone marrow examination
Death in aplasia	Deaths occurring ≥ 7 days following completion of initial treatment while cytopenic; with an aplastic or hypoplastic bone marrow obtained within 7 days of death, without evidence of persistent leukemia
Death from indeterminate cause	Deaths occurring before completion of therapy, or < 7 days following its completion; or deaths occurring ≥ 7 days following completion of initial therapy with no blasts in the blood, but no bone marrow examination available
Relapse ²	Bone marrow blasts ≥ 5 percent; or reappearance of blasts in the blood; or development of extramedullary disease

[figure not shown]
¹ All criteria need to be fulfilled; marrow evaluation should be based on a count of 200 nucleated cells in an aspirate with spicules; if ambiguous, consider repeat exam after 5 to 7 days; flow cytometric evaluation may help to distinguish between persistent leukemia and regenerating normal marrow; a marrow biopsy should be performed in cases of dry tap, or if no spicules are obtained; no minimum duration of response required.

² In cases with low blast percentages (5 to 10 percent), a repeat marrow should be performed to confirm relapse. Appearance of new dysplastic changes should be closely monitored for emerging relapse. In a patient who has been recently treated, dysplasia or a transient increase in blasts may reflect a chemotherapy effect and recovery of hematopoiesis. Cytogenetics should be tested to distinguish true relapse from therapy-related MDS/AML.
Source: [Cheson et al 2003](#).

[figure not shown]
CONFIDENTIAL

CONFIDENTIAL

[figure not shown]
CONFIDENTIAL

CONFIDENTIAL

[figure not shown]
CONFIDENTIAL

CONFIDENTIAL

[figure not shown]
CONFIDENTIAL

CONFIDENTIAL

[figure not shown]
CONFIDENTIAL

CONFIDENTIAL

[figure not shown]
CONFIDENTIAL

CONFIDENTIAL

[figure not shown]
CONFIDENTIAL

CONFIDENTIAL

[figure not shown]
CONFIDENTIAL

CONFIDENTIAL

[figure not shown]
CONFIDENTIAL

CONFIDENTIAL

[figure not shown]
CONFIDENTIAL

CONFIDENTIAL

[figure not shown]
CONFIDENTIAL

CONFIDENTIAL

CONFIDENTIAL

CONFIDENTIAL

CONFIDENTIAL

CONFIDENTIAL

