2.3. Study Endpoints

2.3.1. Primary Endpoints

- Safety and tolerability will be assessed by monitoring frequency, duration, and severity of AEs and DLTs; through physical examinations; by evaluating changes in vital signs and ECGs; and through clinical laboratory blood and urine sample evaluations.
- Part 4 only: ORR, defined as the proportion of subjects who achieve CR or CRi.

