APPENDIX B. INTERNATIONAL WORKING GROUP RESPONSE CRITERIA FOR ACUTE MYELOID LEUKEMIA

Response Category	Response Definition
Complete remission (CR) ¹	Bone marrow blasts < 5 percent; absence of blasts with Auer rods; absence of extramedullary disease; absolute neutrophil count > $1.0 \times 10^9/L$ (1000/ μ L); platelet count > $100 \times 10^9/L$ (100,000/ μ L); independence of red cell transfusions
CR with incomplete recovery (CRi)	All CR criteria except for residual neutropenia (< $1.0 \times 10^9/L$ [1000/ μ L]) or thrombocytopenia (< $100 \times 10^9/L$ [100,000/ μ L])
Morphologic leukemia-free state	Bone marrow blasts < 5 percent; absence of blasts with Auer rods; absence of extramedullary disease; no hematologic recovery required
Partial remission (PR)	All hematologic criteria of CR; decrease of bone marrow blast percentage to 5 to 25 percent; and decrease of pretreatment bone marrow blast percentage by at least 50 percent
Cytogenetic CR (CRC)	Reversion to a normal karyotype at the time of morphologic CR (or CRi) in cases with an abnormal karyotype at the time of diagnosis; based on the evaluation of 20 metaphase cells from bone marrow
Molecular CR (CRm)	No standard definition; depends on molecular target
Treatment failure	
Resistant disease (RD)	Failure to achieve CR or CRi or PR (Phase 1 trials); only includes patients surviving ≥ 7 days following completion of initial treatment, with evidence of persistent leukemia by blood and/or bone marrow examination
Death in aplasia	Deaths occurring ≥ 7 days following completion of initial treatment while cytopenic; with an aplastic or hypoplastic bone marrow obtained within 7 days of death, without evidence of persistent leukemia
Death from indeterminate cause	Deaths occurring before completion of therapy, or < 7 days following its completion; or deaths occurring ≥ 7 days following completion of initial therapy with no blasts in the blood, but no bone marrow examination available
Relapse ²	Bone marrow blasts ≥ 5 percent; or reappearance of blasts in the blood; or development of extramedullary disease

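### A remission with a neutrophil or platelet count exactly at its limit, and none below, is neither CR nor CRi as written, so it can drop out of the CR + CRi primary ORR

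*Protocol*

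**What the plan says.** - **CR** (Protocol Appendix D) requires, besides the marrow, extramedullary and transfusion criteria, "absolute neutrophil count > 1.0" and "platelet count > 100" (both × 10⁹/L). Footnote 1 requires every criterion to be met.
- **CRi** in the same table is "All CR criteria except for residual neutropenia (< 1.0" × 10⁹/L) or "thrombocytopenia (< 100" × 10⁹/L). SAP Appendix B repeats the rule: "All CR criteria except for residual neutropenia (<" and the same limits.
- **MLFS** has the marrow and extramedullary criteria, with "no hematologic recovery required".
- **Primary endpoint.** SAP 2.3.1 gives "ORR, defined as the proportion of subjects who achieve CR or CRi" for Part 4. Protocol 2.2.1 and 9.4.1 agree.
- **AML analysis rule.** SAP 7.4.1.2.1 defines a responder more widely, adding MLFS, PR and peripheral blood blast response to CR and CRi.
- **Assignment.** Under SAP 7.4.1.1 the investigator determines the response. SAP 7.4.1.2.1 takes the best response up to and including the first event. Footnote 1 of the response table sets no minimum duration.

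**The concern.** The CR and CRi limits do not meet. A value equal to a limit satisfies neither inequality, and neither appendix says where it belongs. Read literally, the primary endpoint is then not monotone in the counts. With platelets at 150 and all else qualifying, neutrophils of 0.9 give CRi (a response), 1.0 gives MLFS (not a response under CR + CRi), and 1.1 gives CR (a response).

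Under the CR + CRi definition the gap can only remove responders, so any bias in ORR is downward. The Part 4 AML cohorts are judged on small counts: a cohort stops with 3 or fewer responders of 13, and the regimen is judged futile with 12 or fewer of 43. At either threshold a single classification decides the result. Two sites could also code the same record differently, because no rule covers the boundary value.

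**Working it through.** **Inputs.** Count limits: Protocol Appendix D and SAP Appendix B. Design: p0 = 20%, p1 = 40%, n1 = 13, r1 = 3, n = 43, r = 12, 1-sided alpha 0.05, power 80% (Protocol 9.2.4 and Table 23; SAP 3.2.4.1 and 7.2). Stated early-termination probabilities: 0.7473 and 0.1686 (Protocol 9.5; SAP 11).

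**1. Reproduce the design.** With b(n, x, p) the binomial probability:

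- PET(p) = Σ b(13, x, p) for x = 0 to 3
- P(reject) = Σ b(13, x, p) · P(X2 ≥ 13 − x), for x = 4 to 13, with X2 ~ Bin(30, p)

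At p = 0.40, PET = 0.0013 + 0.0113 + 0.0453 + 0.1107 = 0.1686. At p = 0.20, PET = 0.7473. The rejection probability is 0.0496 at 20% and 0.8002 at 40%. All agree with the plan.

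**2. Classify the counts literally.** The subject meets all other CR criteria.

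| Neutrophils (× 10⁹/L) | Platelets 99 | Platelets 100 | Platelets 101 |
|---|---|---|---|
| 0.9 | CRi | CRi on a lenient reading | CRi |
| 1.0 | CRi on a lenient reading | neither: MLFS | neither: MLFS |
| 1.1 | CRi | neither: MLFS | CR |

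The clear gap is a count at its limit with no count below its limit. Examples are neutrophils 1.0 with platelets 150, and platelets 100 with neutrophils 1.5. Where the other count is below its limit, CRi is arguable.

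**3. Effect on the design.** Neither document says how often counts fall exactly on a limit. As an assumption, let a share q of true CR/CRi responders be lost permanently. The observed rate is then p(1 − q), and the formulas in step 1 give:

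| q | Observed ORR at true 40% | PET | Power | Expected responders lost of 43 (43 × 0.40 × q) | Rejection probability at true 20% |
|---|---|---|---|---|---|
| 0 | 40.0% | 0.1686 | 0.8002 | 0 | 0.0496 |
| 1% | 39.6% | 0.1761 | 0.7896 | 0.17 | 0.0463 |
| 2% | 39.2% | 0.1838 | 0.7785 | 0.34 | 0.0432 |
| 5% | 38.0% | 0.2083 | 0.7424 | 0.86 | 0.0348 |

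Type I error falls with q, so the gap cannot create a false positive.

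**4. When one subject decides.** Losing one responder changes the Stage 1 decision only if there are exactly 4. That probability is b(13, 4, 0.40) = 0.184, or 0.154 at 20%. The probability of continuing and ending with exactly 13 of 43 is 0.033 at 40% and 0.023 at 20%.

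**5. The two ORR definitions.** Under SAP 2.3.1 (CR + CRi), an exact-limit remission coded MLFS is a non-responder. Under SAP 7.4.1.2.1 the same subject is a responder. Which text governs decides whether the gap touches the ORR.

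**The case against.** The strongest reply is that nobody need be lost.

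- **SAP 7.4.1.2.1 keeps the subject.** True as written. But that section contradicts the primary endpoint in both documents, so it cannot serve as a safeguard. If it is aligned with CR + CRi, the gap takes effect. If it stands, the ORR is unaffected but the subject is still labelled MLFS in the best-response table.
- **The investigator assigns response.** This stands. No derivation of AML response from counts by program is described, and an investigator may well record CR or CRi at the boundary. Loss requires that MLFS be chosen.
- **Later visits rescue the subject.** This largely stands for the final analysis. With best response over visits and no minimum duration, loss needs every qualifying assessment before the first event to sit at a limit. The protection is weaker at the interim, which is triggered by the first postbaseline marrows (Protocol 9.4.1 and 9.5; SAP 11). Late Stage 1 subjects may have only one assessment by then. Those sections fix when the analysis happens and do not confine response to that marrow.
- **Exact-limit counts may be rare.** This cannot be settled. The documents give no distribution or reporting precision, and the criteria also print the limits per microlitre, where an exact match is less likely.

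A reader might infer that responders will certainly be lost, or that power drops by several points. The documents support neither. The 5% row, with power 74.2%, needs permanent loss of 5% of responders. Treating a frequency at one assessment as permanent loss ignores the later visits.

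**Conclusion.** The gap is real, is in both documents, and affects the classification behind the primary endpoint. An otherwise qualifying remission with a count exactly at a limit and none below is literally MLFS, and under CR + CRi it can be lost although lower counts would have counted. The conclusion is that it can be lost, not that it is.

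The size is probably small. On the assumption of 1% to 2% permanent loss, power at a true 40% goes from 80.0% to 79.0% or 77.8%, and early termination from 0.169 to 0.176 or 0.184. The assumed shares have no source in the documents. The practical exposure is a cohort at 3 versus 4 responders of 13 in Stage 1. None of the plan's stated design figures is wrong.

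The conflict between SAP 2.3.1 and SAP 7.4.1.2.1 over which categories count as response is the larger matter, and it must be resolved for this one to have a definite answer.

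**What to change.** 1. In Protocol Appendix D and SAP Appendix B, make the limits complementary. For example, let CRi be all other CR criteria met with neutrophils ≤ 1.0 × 10⁹/L or platelets ≤ 100 × 10⁹/L, leaving CR as it is. Note this as the study's operational convention, since the table is presented as published criteria. Moving the boundary value into CR instead gives the same ORR. The ≤ wording also settles the cases with one count at its limit and the other below.
2. In the same edit, align the responder definition in SAP 7.4.1.2.1 with the CR + CRi primary endpoint. Any wider response rate can be reported under a separate name.
3. Tell sites the boundary rule before response is coded for Stage 1.

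The cost is two symbols in each of two tables, one corrected definition in the SAP and a note to sites. No new data are needed, and p0, p1, the sample sizes and the stopping rules stay as they are.
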